9.4 Safety and Tolerability Assessments

9.4.1 Adverse events

Where changes in severity are recorded in the Case Report Form (CRF), each separate severity of the adverse event (AE) will be reported in the listings, only the most severe will be used in the summary tables. A pre-existing condition is defined as an AE that starts before the patient has provided written informed consent and is ongoing at consent. A non-treatment emergent AE is defined as an AE which starts after informed consent but prior to the first dose. A treatment-emergent AE is defined as an AE which occurs postdose or which is present prior to the first dose and becomes more severe postdose.

All AEs will be listed. Treatment-emergent AEs will be summarized by treatment, severity and relationship to the study drug. The frequency (the number of adverse events, the number of patients experiencing an adverse event and the percentage of patients experiencing an adverse event) of treatment-emergent adverse events will be summarized by treatment, Medical Dictionary for Regulatory Activities (MedDRA) version 20.0 system organ class and preferred term. The summary and frequency adverse event tables will be presented for all causalities and those considered related to the study drug. Any serious adverse events will be tabulated.

9.4.2 Concomitant medication

Concomitant medication will be coded using the WHO drug dictionary (Version March 2017 Enhanced Dictionary Version B2 Format). Concomitant medication will be listed.

9.4.3 Clinical laboratory parameters

eGFR will be calculated as:

$$\text{GFR(male)} = 194 * \text{Scr}^{-1.094} * \text{age}^{-0.287}$$

$$\text{GFR(female)} = \text{GFR(male)} * 0.739$$

All clinical chemistry, hematology, urinalysis, urine albumin/creatinine ratio (UACR), eGFR, HbA1c and endocrinology data will be listed. Additionally clinical chemistry, hematology, urinalysis, urine albumin/creatinine ratio (UACR), eGFR, HbA1c and endocrinology data outside the reference ranges will be listed.

Values for any clinical chemistry, hematology, urinalysis, urine albumin/creatinine ratio (UACR), eGFR, HbA1c and endocrinology values outside the reference ranges will be flagged on the individual patient data listings.

9.4.4 Vital signs

Where two or more repeat measurements are performed for vital signs, the median of the original and the repeat values will be used in all subsequent calculations. Where only one repeat measurement is performed for vital signs, the repeat value will be used in all subsequent calculations.

Vital signs data will be summarized by treatment together with changes from baseline, where baseline is defined as Day 1 predose within each period. Figures of mean vital signs and mean changes from baseline profiles by treatment will be presented by treatment. Furthermore, values for individual patients will be listed.

Changes from baseline (predose) will be calculated for vital signs.

9.4.5 Satiety after Standardized Test Meal

A visual analogue scale (VAS) test will be performed to measure perception of satiety (full and hungry). Data will be summarized by treatment and listed along with mean plots showing the profiles for fullness and hunger by treatment and time.

9.4.6 Hypoglycemic Episodes

Hypoglycemic episodes will be listed.

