**Table GBGK.1. Objectives and Endpoints**

Objectives	Endpoints

Primary The primary objective of this study is to evaluate glucodynamic effects of dulaglutide 0.75 mg compared with placebo in area under the glucose concentration versus time curve from 0 to 4 hours (glucose AUC[0-4h]) at 4 weeks in Japanese patients with T2D.
	
 
The change from baseline in glucose AUC(0-4h) at 4 weeks
 

Secondary To evaluate pharmacodynamic (PD) effects of dulaglutide 0.75 mg compared with placebo at 4 weeks.
	
 
The change from baseline in fasting blood glucose at 4 weeks
 
The change from baseline in postprandial blood glucose at 4 weeks
 
The change from baseline in insulin at 4 weeks
 
The change from baseline in c-peptide at 4 weeks
 
The change from baseline in glucagon at 4 weeks
 
The change from baseline in triglyceride at 4 weeks
 

To evaluate safety and tolerability of dulaglutide 0.75 mg for 4 weeks
	
 
Treatment-emergent adverse events (TEAEs)
 
Incidence of hypoglycemic episodes
 

Tertiary/Exploratory Objectives To evaluate daily glucose variability
	
 
Time course of daily average glucose by CGM during the first week
 

To evaluate satiety after standardized test meal
	
 
The change from baseline in satiety (full and hungry) in visual analog scale (VAS) at 1, 2, and 4 weeks
 

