### 7.5. Special Treatment Considerations

#### 7.5.1. *Management of Increased Hypoglycemia Risk*

If a hypoglycemic event occurs, the patient should record in the study diary the episode and associated symptoms and/or signs, and rescue treatment (if taken).

Study site personnel will record information related to hypoglycemia such as start and end date and time of the episode, hypoglycemia signs and symptoms present. Following definitions and criteria will be used for categorizing an episode considered to be related to hypoglycemia (the PG values in this section refer to values determined by a laboratory or International Federation of Clinical Chemistry and Laboratory Medicine plasma-equivalent glucose meters and strips) (American Diabetes Association 2005):

- **Documented symptomatic hypoglycemia** is defined as any time a patient feels that he/she is experiencing symptoms and/or signs associated with hypoglycemia, and has a PG level of  $\leq 70$  mg/dL ( $\leq 3.9$  mmol/L).
- **Asymptomatic hypoglycemia** is defined as an event not accompanied by typical symptoms of hypoglycemia but with a measured PG of  $\leq 70$  mg/dL ( $\leq 3.9$  mmol/L).
- **Probable symptomatic hypoglycemia** is defined as an event during which symptoms of hypoglycemia are not accompanied by a PG determination (but that was presumably caused by a PG concentration of  $\leq 70$  mg/dL [ $\leq 3.9$  mmol/L]).
- **Severe hypoglycemia** is defined as an episode requiring the assistance of another person to actively administer carbohydrate, glucagon, or other resuscitative actions. These episodes may be associated with sufficient neuroglycopenia to induce seizure or coma. Plasma glucose measurements may not be available during such an event, but neurological recovery attributable to the restoration of PG to normal is considered sufficient evidence that the event was induced by a low PG concentration.
- **Nocturnal hypoglycemia** is defined as any hypoglycemic event that occurs between bedtime and waking.

If a hypoglycemic event meets the criteria of severe, it needs to be recorded as serious on the adverse event (AE) CRF and reported to Lilly as a serious adverse event (SAE).

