#### **9.2.2.2. C-Cell Hyperplasia and C-Cell Neoplasms**

Individuals with personal or family history of certain thyroid or nonthyroid endocrine abnormalities or certain preexisting laboratory and genetic characteristics will be excluded from the study (see Section 6.2). The assessment of thyroid safety during the trial will include reporting of thyroid TEAEs and measurements of calcitonin according to the Study Schedule (Section 2) at Visit 3, 7, 9, 13, and ET visit. The purpose of calcitonin measurements is to assess the potential of dulaglutide versus placebo to affect the thyroid C-cell function, which may indicate development of C-cell hyperplasia and neoplasms.

Patients who develop serum calcitonin increases  $\geq 50\%$  of the mean of the baseline and screening values AND an absolute value  $\geq 20$  pg/mL and  $< 35$  pg/mL at Visit 13 will be asked to repeat the measurement within 1 month. If this repeat value is increasing ( $\geq 10\%$  increase), the patient will be recommended that he or she undergo additional endocrine assessment and longer-term follow-up by an endocrinologist to exclude a serious adverse effect on the gland.

Patients with an increase in serum calcitonin  $\geq 50\%$  of the mean of the baseline and screening values AND an absolute value  $\geq 35$  pg/mL at Visit 13 will be recommended to immediately undergo additional endocrine assessments and longer-term follow-up by an endocrinologist.

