#### **10.3.1.2. Statistical Evaluation of Safety**

Safety laboratory parameters and vital signs will be listed, and summarized using standard descriptive statistics. Additional analysis may be performed if warranted upon review of the data.

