9. STATISTICAL METHODOLOGY

9.1 General

Data listings will be provided for all data that is databased. Summary statistics and statistical analysis will only be presented for data where detailed in this SAP. For continuous data, summary statistics will include the arithmetic mean, arithmetic standard deviation (SD), median, min, max and N; for log-normal data the geometric mean and geometric coefficient of variation (CV%) will also be presented. For categorical data, frequency count and percentages will be presented. Data listings will be provided for all patients up to the point of withdrawal, with any patients excluded from the relevant population highlighted. Summary statistics and statistical analyses will generally only be performed for patients included in the relevant analysis population. For the calculation of summary statistics and statistical analysis, unrounded data will be used.

Mean change from baseline is the mean of all individual patients’ change from baseline values. Each individual change from baseline will be calculated by subtracting the individual patient’s baseline value from the value at the timepoint. The individual patient’s change from baseline values will be used to calculate the mean change from baseline using a SAS procedure such as Proc Univariate.

Data analysis will be performed using SAS® Version 9.3 or greater.

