x_{l-h} = the high point in consecutive BG time points for the M^{th} day (peak)

p = the number of qualifying differences: $(BG_l - BG_{l-h}) \geq 1 \text{ SD}(\text{daily BG values})$ and that follow the direction of the first qualifying difference within the BG time points for the M^{th} day

Daily average, daily standard deviation, and daily MAGE from glucose data will be summarized. Individual (by patient) and mean by treatment of glucose data will be plotted over the days.

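### The SAP only lists hypoglycemic episodes and safety laboratory values where the protocol calls for an incidence and descriptive summaries, and SAP Section 11 declares no change

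*SAP*

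**What the plan says.** **Hypoglycemia.** Protocol Table GBGK.1 (and the synopsis) gives the secondary safety objective two endpoints: treatment-emergent adverse events (TEAEs) and "Incidence of hypoglycemic episodes". Protocol 7.5.1 defines five categories: documented symptomatic, asymptomatic, probable symptomatic, severe and nocturnal. SAP 9.4.6 consists of one sentence: "Hypoglycemic episodes will be listed". SAP 9.1 adds the rule "Summary statistics and statistical analysis will only be presented for data where detailed in this SAP".

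**Laboratory data.** Protocol 10.3.1.2 states "Safety laboratory parameters and vital signs will be listed, and summarized using standard descriptive statistics". Protocol 9.2.2.2 explains one of these tests: "The purpose of calcitonin measurements is to assess the potential of dulaglutide versus placebo to affect the thyroid C-cell function". Protocol 9.2.2.1 says amylase and lipase are measured to look for effects of dulaglutide on the exocrine pancreas. In SAP 9.4.3, "eGFR, HbA1c and endocrinology data will be listed", as are the other safety laboratory panels. Out-of-range values are listed again and flagged. No summary is described.

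**Declared changes.** SAP Section 3 says the SAP supersedes the protocol's statistical section and that substantial differences will be identified. SAP Section 11 declares none.

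**The concern.** A listing shows each event or value but gives no numerator over a denominator, so it does not report an incidence. One of the two named endpoints of the safety objective therefore has no dedicated output. Exploratory satiety, by contrast, is summarized by treatment with plots (SAP 9.4.5), and vital signs are summarized by treatment with change from baseline (SAP 9.4.4).

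For laboratory values, the SAP drops a summary that the protocol specifies. The cross-over gives each completer a value under dulaglutide and one under placebo. A shift in calcitonin, amylase or lipase that stays within the reference range would sit unflagged in a listing and appear in no table.

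Section 11 matters separately. A reader who relies on it would conclude that the protocol's safety analyses are carried over intact.

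**Working it through.** **1. The plan's own figure.** Neither document states a figure for hypoglycemia or laboratory data. The only computed figure is 93% power for the primary glucose AUC comparison. Inputs from Protocol 10.1 and SAP Section 7: difference 190, SD 140, correlation 0.3, one-sided 0.025, n = 11.
- SD of the within-patient difference = 140 × √(2 × (1 − 0.3)) = 165.65
- Noncentrality = 190 / (165.65 / √11) = 3.804
- Paired t-test power = 92.8% with 10 df (92.2% with 9 df)

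The figure reproduces, but it has no bearing on the safety outputs.

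**2. Endpoint to output, hypoglycemia.** The chain is Table GBGK.1 (incidence), Protocol 7.5.1 (categories), SAP 9.4.6 (listing) and SAP 9.1 (no summary unless detailed). No step yields a count of affected patients by treatment. The nearest substitute is the TEAE tables in SAP 9.4.1, which give events, patients and percentages by treatment, system organ class and preferred term. An episode entered as an adverse event would be counted there. Two limits remain. Those tables are not organized by 7.5.1 category. Also, the Schedule of Activities has separate rows for adverse events and hypoglycemia, and neither document says that every episode is entered as an adverse event, so a preferred-term row need not equal the incidence.

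**3. Specification to output, laboratory data.** Protocol 10.3.1.2 has two parts, listing and descriptive summary, and SAP 9.4.3 keeps only the first. The same protocol sentence covers vital signs, for which SAP 9.4.4 keeps both parts, using Day 1 predose of each period as baseline.

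**4. Are the data there?** Appendix 6 schedules safety blood samples on Days 1, 29, 57 and 85, before dosing on Days 1 and 57. With screening, that is 1 + (2 periods × 2) = 5 samples, matching the five in Appendix 5. Each completer therefore has a change from the same period's Day 1 under each treatment.

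**5. What the incidence table could show.** Exact (Clopper-Pearson) two-sided 95% limits:
- 0 of 12: upper limit = 1 − 0.025^(1/12) = 26.5%
- 0 of 11: upper limit = 1 − 0.025^(1/11) = 28.5%
- 1 of 12 = 8.3%: limits 0.2% to 38.5%

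The documents give no expected incidence. For assumed true values of 2%, 5%, 10% and 20%, the chance of at least one affected patient among 12, 1 − (1 − p)^12, is 21.5%, 46.0%, 71.8% and 93.1%. An exact McNemar comparison would need at least 6 discordant patients, all in one direction, for two-sided p < 0.05 (2 × 0.5^6 = 0.031; five give 2 × 0.5^5 = 0.0625). The table is therefore descriptive.

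**The case against.** The strongest defense is that the safety objective is largely covered. TEAEs are tabulated by treatment, serious events are tabulated, and vital signs are summarized. Protocol 9.2 has sites record any adverse event, and Protocol 9.4.5 counts hypoglycemia among adverse events for review. Protocol 10.3.1.1 makes safety summaries depend on event frequency, and few episodes may be expected. Laboratory values are not a named endpoint, and out-of-range values are flagged.

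Much of this stands, and it limits the point. It does not remove it. The SAP attaches no frequency condition to hypoglycemia, and SAP 13.3 already says what to present when there are too few data. Separate table shells exist and are not available here, but SAP 9.1 does not let them be assumed to hold a summary that the SAP omits. Protocol 10.3.1.2 plans laboratory summaries whether or not those values are endpoints.

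Several stronger readings are tempting but unsupported:
- **Only severe episodes reach the adverse event tables.** Protocol 7.5.1 says that severe episodes are recorded and reported as serious. It does not exempt the others from adverse event recording.
- **A formal dulaglutide-placebo laboratory comparison was promised.** The protocol promises descriptive statistics, and only calcitonin carries a versus-placebo purpose.
- **Continuous glucose monitoring (CGM) was left unused, contrary to plan.** The protocol plans CGM for exploratory daily glucose, and the SAP uses it for that: "Daily average, daily standard deviation, and daily MAGE from glucose data will be summarized". The 7.5.1 glucose values are "values determined by a laboratory or International Federation of Clinical Chemistry and Laboratory Medicine plasma-equivalent glucose meters and strips", so CGM lies outside the endpoint.
- **Asymptomatic episodes can be found only at meal tests.** This rests on the Schedule of Activities not mentioning home testing. Protocol 7.5.1 provides for meters and a diary, and the documents do not say whether meters are supplied. A coverage percentage from the meal tests would treat seven discrete samples as continuous observation.

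**Conclusion.** The point holds in a limited form. The SAP omits a dedicated incidence for a named secondary endpoint and a descriptive laboratory summary that the protocol specifies, and Section 11 is wrong to declare no change. A reader might infer that the safety objective goes unanswered. It does not, because its other endpoint is tabulated by treatment and some or all hypoglycemic episodes may appear in those tables.

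The effect is on reporting only: two sets of descriptive tables and one statement. The primary analysis and its power are unaffected. With 11 or 12 patients, even zero episodes would leave an upper limit of 26.5% to 28.5%, so the tables would inform without settling any treatment difference. The conclusion assumes that SAP 9.1 is applied as written and that the table shells add no summary beyond the SAP.

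**What to change.** 1. **SAP 9.4.6:** tabulate by treatment the number and percentage of patients with an episode and the number of episodes, overall and for each Protocol 7.5.1 category. The denominator is the Safety population patients who received that treatment. Nocturnal is defined by timing and can overlap the other categories, so the categories should not be summed. If precision is to be shown, add exact 95% limits.
2. **SAP 9.4.3:** add descriptive summaries by treatment of laboratory values, including calcitonin, amylase and lipase, with change from the same period's Day 1 value, following SAP 9.4.4.
3. **SAP Section 11:** correct the statement. If either output is deliberately kept as a listing, declare that as a change and give the reason.

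Optional: a low-glucose summary from CGM, labeled exploratory and kept apart from the 7.5.1 categories. It would need its own window, because the SAP's window of Day -1 to Day 6 holds only five full days after the Day 1 dose (Days 2 to 6; 5/28 = 18% of the period). Its absence is not a departure from the plan.

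Cost: SAP wording and a few descriptive tables, with no new data, visits or patients.

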9.4.7 Hepatic Monitoring

If a patient experiences elevated alanine aminotransferase (ALT) $\geq 3 \times$ upper limit of normal (ULN), alkaline phosphatase (ALP) $\geq 2 \times$ ULN, or elevated total bilirubin (TBL) $\geq 2 \times$ ULN, liver tests will be performed to confirm the abnormality.

If a patient has a liver abnormality then they will be included in the listings and summaries detailed below.

The patients' liver disease history and associated person liver disease history data will be listed. Any concomitant medication of acetaminophen/paracetamol will be listed. Results from any hepatic monitoring procedures, such as a magnetic resonance elastography (MRE) scan, and a biopsy assessment will be listed, if performed.

Hepatic risk factor assessment data will be listed. Liver related signs and symptoms data will be summarized in a frequency table by treatment and will also be listed. Alcohol and recreational drug use data will also be listed.

All hepatic chemistry, hematology, coagulation, and serology data will be listed. Values outside the reference ranges will be flagged on the individual patient data listings.

9.4.8 Other assessments

All other safety assessments not detailed in this section will be listed but not summarized or statistically analyzed.

9.4.9 Safety and Tolerability Statistical Methodology

No inferential statistical analyses are planned.

10. INTERIM ANALYSES

No interim statistical analyses are planned.

11. CHANGES FROM THE PROTOCOL SPECIFIED STATISTICAL ANALYSES

There were no changes from the protocol specified statistical analyses.

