**Statistical Analysis:**

The PD parameters on Weeks 0, 1, 2, and 4 will be analyzed using a mixed-effects linear model. The PD parameters for glucose, insulin, glucagon, c-peptide, and triglyceride that will be statistically evaluated include area under the curve, fasting and postprandial values at each time point. The model will include treatment, sequence, day, and treatment-by-day interaction as fixed effects, baseline as covariate, and patient as random effect. The baseline is the predose value on Day 1. The least squares means and the 95% confidence intervals (CIs) by treatment group will be tabulated and plotted. Comparisons between dulaglutide and placebo will be performed. Difference of least squares means of dulaglutide to placebo, and the 95% CIs, will be tabulated.

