##### **10.3.3.2. Pharmacodynamic Statistical Inference**

The PD parameters on Weeks 0, 1, 2, and 4 will be analyzed using a mixed-effects linear model. The PD parameters for glucose, insulin, glucagon, c-peptide, and triglyceride that will be statistically evaluated include AUC, fasting and postprandial values at each time point. The model will include treatment, sequence, day, and treatment-by-day interaction as fixed effects, baseline as covariate, and patient as random effect. The baseline is the predose value on Day 1. The least squares means and the 95% CIs by treatment group will be tabulated and plotted. Comparisons between dulaglutide and placebo will be performed. Difference of least squares means of dulaglutide to placebo, and the 95% CIs, will be tabulated.

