9.3.2 Pharmacodynamic Statistical Methodology

All PD parameters will be listed and summarized by treatment group and week. Individual observed and changes from baseline in glucose, insulin, glucagon, C-peptide, and triglyceride concentrations will be listed and summarized and their mean time profiles will be plotted by treatment group together with changes from baseline.

PD AUCs and iAUCs on Weeks 0, 1, 2, and 4 will be analyzed using a mixed-effects linear model for glucose, insulin, glucagon, C-peptide, and triglyceride . The model will include

treatment, sequence, period, week and treatment-by-week interaction as fixed effects, baseline as a covariate and patient as random effect.

The least squares means and the 95% CIs by treatment group will be tabulated and plotted. Comparisons between dulaglutide and placebo will be performed. Difference of least squares means of dulaglutide to placebo, and the 95% CIs, will be tabulated. Example SAS code is given below:

```
proc mixed data=pd;
class patient treatment sequence period week;
model pd = baseline treatment sequence period week treatment*week / ddfm=kr;
repeated week(treatment) / subject=patient type=un;
lsmeans treatment*week / pdiff alpha=0.05;
run;
```

The repeated patient effect models the within-patient errors using an unstructured variance-covariance matrix. If the analysis fails to converge, the following variance-covariance matrix will be used (in order) until one converges:

1. compound symmetry,
2. banded, and then
3. first-order autoregressive.

Continuous plasma glucose monitoring (CGM)

For the CGM data, parameters will be derived from the raw data collected through Day -1 to Day 6 (7 days), of CGM device use by patient and treatment.

The following notation will be used in the definition:

- n represents the number of time points within a day
- i represents a time point within a day
- m represents a day

Within-day glucose SD:

$$SD_m = \sqrt{\frac{\sum_{i=1}^n (BG_i - \left\{ \frac{\sum_{i=1}^n BG_i}{n} \right\})^2}{n-1}}$$

Mean amplitude of glycemic excursions (MAGE):

this parameter is calculated based on the arithmetic mean of differences between consecutive peaks and nadirs of differences greater than one SD of mean glycemia. Mean of the differences between consecutive peaks and nadirs in BG that meet qualifying criteria

$$MAGE_m = \frac{\sum_{l=1}^p |BG_l - BG_{l-h}|}{p}$$

where,

x_l = the low point in consecutive BG time points for the M^{th} day (nadir)

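### SAP 11 declares no changes, but SAP 9.3.2 limits the protocol's mixed model to AUCs and so leaves fasting glucose with no modelled contrast against placebo

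*SAP*

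**What the plan says.** Protocol 10.3.3.2 sets out a mixed-effects linear model for five analytes (glucose, insulin, glucagon, c-peptide, triglyceride) and names the parameters "that will be statistically evaluated include AUC, fasting and postprandial values at each time point". The synopsis agrees: "that will be statistically evaluated include area under the curve, fasting and postprandial values at each time point". The promised output is explicit: "Difference of least squares means of dulaglutide to placebo, and the 95% CIs, will be tabulated". On the model terms, the protocol says "The model will include treatment, sequence, day, and treatment-by-day interaction as fixed effects", with baseline as covariate and patient as random effect.

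SAP 9.3.2 is narrower: "PD AUCs and iAUCs on Weeks 0, 1, 2, and 4 will be analyzed using a mixed-effects linear model". For the time-point values it says "Individual observed and changes from baseline in glucose, insulin, glucagon, C-peptide, and triglyceride concentrations will be listed and summarized", with mean profiles plotted by treatment. Its model terms are "treatment, sequence, period, week and treatment-by-week interaction as fixed effects", so period is new.

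SAP Section 11 then reads: "There were no changes from the protocol specified statistical analyses".

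Two rules in the SAP settle how these texts interact. Section 3 gives the SAP precedence over the protocol's statistical considerations and undertakes to identify substantial differences. Section 9.1 confines summaries and statistical analyses to those the SAP sets out.

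**The concern.** Fasting glucose at 4 weeks is a named secondary endpoint in Protocol Table GBGK.1, under an objective framed as a comparison with placebo. Protocol 9.6.2 and SAP 9.3.1 also list it at 1, 2 and 4 weeks. If the SAP is followed as written, the report will hold means by treatment for this endpoint but no adjusted difference from placebo and no confidence interval.

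The study is blinded to patients only. A fasting-glucose contrast added later would enter as a supplementary analysis under SAP 3, although the protocol had specified it from the start. And because Section 11 says nothing changed, the SAP gives its reader no signal that a protocol-specified comparison is missing.

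**Working it through.** 1. **The plan's own figure.** Protocol 10.1 and SAP 7 assume a difference of 190 mg\*hr/dL, SD 140, intra-patient correlation 0.3, one-sided 0.025 and 11 completers.
   - SD of the within-patient difference = 140 × √(2 × (1 − 0.3)) = 140 × √1.4 = 165.65.
   - Noncentrality = 190 / (165.65 / √11) = 190 / 49.95 = 3.804.
   - Power from the noncentral t is 92.8% with 10 degrees of freedom and 92.2% with 9, against 93% stated.
   - The figure reproduces. It concerns glucose AUC(0-4h), which SAP 9.3.2 still models, so nothing below changes it.

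2. **The two scopes side by side.**

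| Item | Protocol 10.3.3.2 | SAP 9.3.2 |
|---|---|---|
| AUC, five analytes | Modelled, difference and CI | Modelled, difference and CI (incremental AUC too) |
| Fasting glucose | Modelled, difference and CI | Descriptive only |
| Postprandial glucose by time point | Modelled, difference and CI | Descriptive only |
| Time-point insulin, c-peptide, glucagon, triglyceride | Modelled, difference and CI | Descriptive only |
| Period as fixed effect | No | Yes |

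3. **Does the protocol fill the gap?** No. SAP 3 puts the SAP above the protocol on statistics, and SAP 9.1 excludes analyses that the SAP does not detail. The response in the example SAS code has a generic name, but the sentence introducing the model names AUCs and incremental AUCs. Nor does the protocol amendment explain the difference: the changes listed in Protocol Appendix 7 do not touch Section 10.

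4. **Do the AUC models stand in for the endpoints?**
   - Fasting glucose: no. The premeal value feeds the AUC, the incremental adjustment and the baseline, but it has no AUC of its own. Lost contrasts: 1 value × 3 weeks = 3.
   - Postprandial glucose: only indirectly. Protocol 9.6.2 defines it as the values at 30, 60, 90, 120, 180 and 240 minutes and lists glucose AUC separately. Lost contrasts: 6 × 3 = 18.
   - The other four analytes: partly. Protocol 9.6.2 lists both time-point values and AUC(0-4h) for each, and the AUC contrasts stay.

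5. **Do the descriptive summaries substitute?** Not fully. In a cross-over the CI for the difference needs the SD of within-patient differences, SD × √(2 × (1 − ρ)) with equal SDs. Means and SDs by treatment do not carry ρ. A reader would have to rebuild the interval from the individual listings.

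6. **Other differences missing from SAP 11.** Protocol 10.3.1.2 says safety laboratory parameters are both listed and summarized; SAP 9.4.3 lists and flags them only. The endpoint in Table GBGK.1 is the incidence of hypoglycemic episodes; SAP 9.4.6 provides a listing only.

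7. **A check on the remedy.** SAP 9.3.1 defines baseline as the premeal Day 1 value of the period, so for fasting glucose the Week 0 response equals the covariate. A simulated set of 11 patients × 2 periods, fitted with the SAP's fixed effects at Week 0, gave a baseline slope of 1 and a largest residual of about 1e-13. Two of the eight treatment-by-week variances can then go to zero, which makes an unstructured fit degenerate. (The joint unstructured fit was not run.) Leaving Week 0 out also cuts the covariance parameters from 8 × 9 / 2 = 36 to 6 × 7 / 2 = 21.

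**The case against.** The best defence is that no sentence in the SAP withdraws these contrasts. They are specified in the protocol; SAP 3 says analyses generally rest on the protocol unless modified by agreement; SAP 9.3.1 says the secondary measures, fasting glucose included, will be evaluated; and Section 11 affirms that nothing changed. On that view the SAP is merely incomplete, and the table shells, which are not among the documents, may contain the missing outputs.

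Part of this stands. A reader might infer that the sponsor chose to remove the comparison, but the documents do not show intent, and incomplete drafting fits them as well. What fails is the idea that the protocol or the shells repair the omission. SAP 9.1 limits analyses to those detailed in the SAP, and the only methods the SAP details for time-point values are descriptive. On either view SAP 9.3.2 and SAP 11 cannot both be right about the protocol.

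A second objection is that so many time-point contrasts in about 11 patients add little. That is a fair reason to keep postprandial values descriptive, but it has to be declared, and it does not cover fasting glucose.

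On hypoglycemia, Protocol 10.3.1.1 summarizes safety data only where event frequency permits, and SAP 9.4.1 tabulates adverse events. That is partial cover: Protocol 7.5.1 expressly requires adverse event recording only for severe episodes. The period term is a reasonable addition to a cross-over model; the fault is only that it is not declared.

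**Conclusion.** The point holds. SAP 11 is incorrect as written, and under the SAP fasting glucose has no modelled difference from placebo at any of its three weeks. Postprandial glucose has none as the protocol defines it. Insulin, c-peptide, glucagon and triglyceride keep theirs through AUC and lose it for time points.

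The consequence is moderate. Changes from baseline are still summarized by treatment, SAP 3 allows supplementary analyses if they are identified in the report, and the primary analysis and its power stand.

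Two stronger readings should be resisted. A reader might count every time point at every week and conclude that most of the secondary analysis has been lost. Those cells are correlated, the Table GBGK.1 secondary PD endpoints are at 4 weeks, and four of them keep an AUC contrast. A reader might also infer that the postprandial baseline must be redefined. SAP 9.3.1 sets one premeal baseline for all PD parameters, and curing this omission does not require changing it.

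The conclusion assumes that SAP 3 and 9.1 mean what they say. The wording mismatch is certain; what will finally be tabulated is less so without the shells.

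**What to change.** - **SAP 9.3.2:** extend the existing mixed model to fasting glucose and to the other protocol-specified time-point values, reporting dulaglutide-placebo differences with 95% CIs by week. For fasting glucose use Weeks 1, 2 and 4 as the response, since Week 0 is the covariate itself. The covariance fallback order already in 9.3.2 can apply if the unstructured fit fails.
- **Postprandial time points:** if the sponsor prefers to keep them descriptive, say so in SAP 11 and give the reason.
- **SAP 11:** replace the statement of no changes with a list of all remaining differences from the protocol, including the period term.
- **SAP 9.4.3:** add descriptive laboratory summaries.
- **SAP 9.4.6:** add a table of hypoglycemia incidence by treatment (patients, percentages, episodes).

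The cost is SAP wording and some extra tables. All the data are already collected under the protocol, so no visits, samples or design changes are needed.
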